1. INTRODUCTION

1.1 Background

The traditional method of tracheal intubation requires the insertion of a laryngoscope with the left hand into the oral cavity to displace the tongue and directly visualise the glottis.

The “sniffing the morning air” (or “sniffing”) position has been traditionally used for tracheal intubation using direct laryngoscopy. This comprises of flexion of the lower cervical spine, extension at the atlanto-occipital joint and a horizontal level between the tragus of the ear and sternum (Brindley, et al. 2010). The theoretical purpose of this position is to improve the glottic visualisation by aligning the oral, pharyngeal and tracheal axes (Figure 1, B).

[figure not shown]

Figure 1. Traditional head and neck position for tracheal intubation

- A. Normal head position showing 3 axes in supine position.
- B. Sniffing the morning air position with occiput raised showing alignment of 3 axes.
- C. Direct laryngoscopy in the sniffing position.

In recent years with the advancement of technology, videolaryngoscopy has become popular and many centres are now using only videolaryngoscopes for tracheal intubation. Visualisation occurs “indirectly” through fiberoptic or digital channels. Most videolaryngoscopes use two types of blades. The Macintosh type for normal airway and hyper-angulated blade for difficult airway.

Hyperangulated blades such as the Glidescope LoPro (Verathon Inc, Bothwell, WA, USA) (Figure 2 B), McGrath Series 5 X blade (Medtronic, Minneapolis, MN, USA) and Storz C-Mac D-blade (Karl Storz Endoscoke, Tuttlingen, Germany) are more curved than the traditional standard geometry (Mcintosh blades – Figure 2 A) used with direct laryngoscopy and are thought to improve glottis visualisation without significant change in head position. However, visualisation of glottis is one of the three steps involved in videolaryngoscopy assisted tracheal intubation. The other two steps include aligning the tube with the glottic inlet and advancing the tube through the glottis into the trachea.

[figure not shown]

Figure 2. Geometrical comparison of blade types, A: Macintosh (Mac) blades and B: hyper angulated blade

One of the main drawbacks in videolaryngoscopy is that despite good view of glottis on the screen, it can be difficult to successfully advance the tracheal tube into the trachea. Anterior impingement of the tracheal tube at the sub-glottic region is a recognised problem with hyperangulated and channelled videolaryngoscopes (Levitian 2011). VL directs the pre-formed tracheal tube anteriorly but the trachea descends posteriorly into the thorax creating an acute angle impeding passage of the tube (Levitian, et al. 2011). This is demonstrated in figure 3. This can result in difficult intubation or a failed intubation. Manoeuvres such as tube rotation and rotation of bougie (Mendonca, et al. 2018) can rectify this problem to some extent.

Aziz, et al. (2016) found that laryngoscopy was more difficult with hyper-angulated blades in the “sniffing” position compared to neutral position

contradictory to traditional laryngoscopy teaching. Intermediary positions between “sniffing” and supine should be studied as these may balance the needs of maintaining sufficient mouth opening and not hindering angles affecting the axial alignment (Levitin, et al. 2011). Both studies recommend the benefits of a ramped position as it does reduce the time to desaturation and reduces aspiration risk compared to supine neutral positions and should be considered when using hyperangulated blades. Mendonca, et al. (2018) studied neutral and sniffing position with no difference in success rate in tracheal intubation between two positions.

[figure not shown]

Figure 3. A) Acute angle produced by the trajectory of the tube (black arrow) and the trachea (green tube – marked by red arrow). B) Preformed acute angle stylet directing the tube anteriorly leading to anterior impingement.

Using magnetic resonance imaging in awake and healthy patients, Adnet, et al. measured the oral, pharyngeal and tracheal axes using the neutral position, “sniffing” position and simple head extension and found neither position resulted in perfect alignment of the 3 axes. However, they didn’t study the effect of position on angle between tracheal and laryngeal axes. The search for further evidence is necessary for VL as there is a paucity of research in with regard to best head and neck position for videolaryngoscopy.

1.2 Proposed study

This study would assess whether differing head and neck positions would improve alignment between upper airway anatomical axes, in particular the tracheal and laryngeal axes and therefore minimise the possibility of anterior impingement.

1.3 Study population

Staff from University Hospitals Coventry & Warwickshire NHS Trust

1.4 Treatment / Intervention (if applicable)

Magnetic resonance imaging (MRI) can safely be used to assess the upper airway anatomy and would allow measurement of the axes described to suggest which head and neck position would provide best anatomical alignment to reduce anterior impingement.

All the MRI scans will be conducted using 3.0 Tesla (Optima 750w, GE Medical, Milwaukee, WI, USA) using the cervical spine section of the coil. T2-weighted images in the sagittal plane will be acquired using a fast recovery fast spin echo (FRFSE) technique with the parameters in Table 1. The scans will take around two and half minutes and a member of the anaesthetic investigator team will be present to facilitate positional changes and maintain consistency.

Acquisition parameters (Table 1):

Repetition time (TR)	2905 ms
Echo time (TE)	107ms
Field of view (FOV)	36 cm
Slice thickness	3 mm
Slice gap	1 mm
ETL	19
Frequency matrix size	352
Phase matrix size	320
Number of excitations (NEX)	3
Receiver band width	41.67 kHz
Scan time	2 min 34 s

MRI scanning will be performed in following 3 head and neck positions:

Neutral position- Participant lying flat on the MRI table, with a vertical gaze, without any pillow (no flexion, no extension of the neck).

Sniffing position is achieved with head resting on Oxford HELP headrest (Alma Medical, London) of 7cm in height to achieve neck flexion by 35° and extension at atlantooccipital joint to achieve face plane extension of 15° (Horton WA 1989)

Extension position: Oxford HELP Base pillow (Alma Medical, London) is placed under the shoulders with head resting off the end and neck in full extension position.

2. RATIONALE

2.1 Aims and hypothesis

To determine which patient positioning significantly improves the alpha (α) angle. It is defined as the angle between the tracheal axis (TA) and laryngeal axis (LA). This can be seen in Figure 4 below.

Other two angles measured would be:

- Beta (β) angle between the laryngeal axes (LA) and pharyngeal axes (PA)
- Delta (δ) angle between pharyngeal axes (PA) and oral axes (OA)

[figure not shown]

Figure 4. MRI scan showing tracheal, laryngeal axes and pharyngeal axes and corresponding α angle, β angle and δ angle

- The tracheal axis (TA) is defined as a line passing through the centre of intrathoracic part of trachea to the centre of cricoid cartilage.

- The laryngeal axes (LA) is defined as a line passing through the centre of cricoid cartilage to the base of the epiglottis.
- The pharyngeal axis (PA) is defined as a line passing through the anterior portion of the atlas and C2.
- The oral axis (OA) is defined as straight line drawn parallel to the hard palate

2.2 Justification

Videolaryngoscopy (VL) has become a standard of care in anaesthesia and they are included in airway management guidelines. VLs are gradually replacing direct laryngoscopes. For a direct laryngoscopy and tracheal intubation, the sniffing position has been considered as ideal. When this position is transferred to VL, problems such as anterior impingement occur where the tube tip hits the anterior wall of trachea and fails to advance further. Aziz, et al. (2016) found that the "sniffing" position made intubation more difficult than the neutral position. It is therefore critically important to determine what head positions are important to use with VL.

The use of MRI in healthy subjects has been attempted previously to determine the geometrical axes within the oral cavity (Adnet, et al. 2001). These researchers however did not specifically consider the alpha angle we have defined which could reduce anterior impingement with VL. Anterior impingement is an important consideration as it can result in failed intubation and this is clinically important if VL is used as a rescue device in an emergency.

We hypothesise that the position that improves the alpha angle the most would be considered as the ideal position for videolaryngoscopy and tracheal intubation. Due to the widespread and increasing use of videolaryngoscopes, this study would help us to recommend an ideal head and neck position. This will further help to improve the first attempt success rate of tracheal intubation.

2.3 Assessment and management of risk

There are no anticipated risks in undergoing MRI scan. Participants will have to complete the MRI safety checklist and have this reviewed by a radiographer for any risks before they can enter the scanner.

Process if inadvertent abnormality is found: Participants will be asked to consent to any abnormal finding of significance to be reported to their GP

Other considerations:

- Risk of claustrophobia and loud noise can occur during the scan. Ear defenders and an emergency button will be provided as per standard MRI practice.
- Participants will be given the option to withdraw at any stage if they feel that they are not able to tolerate lying down within the MRI Scanner.
- We would also advise participants who are pregnant or who have devices or medical conditions that can be exacerbated by these experiences to not partake.

3. OBJECTIVES AND OUTCOME MEASURES/ENDPOINTS

3.1 Primary objective

- Measurement alpha (α) angle between the tracheal axis (TA) and laryngeal axes (LA) in three different positions.

The primary objective is to identify which of the three head and neck positions we have identified ("sniffing", extension of neck and neutral position) improves the alpha angle when examined under MRI. We hypothesise the position that most improves the alpha angle would reduce the incidence of anterior impingement with videolaryngoscopy. We hypothesise the position that brings the alpha angle closest to 180° would reduce the incidence of anterior impingement and therefore considered best for tracheal intubation using VL.

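### Section 8.3.1 plans only an overall test on alpha, which cannot show which of the three positions is better; it needs within-person contrasts and a naming rule

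*Combined protocol and SAP*

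**What the plan says.** Section 3.1 poses a selection question: "The primary objective is to identify which of the three head and neck positions we have identified" improves alpha, as seen on MRI. Two hypotheses follow: "We hypothesise the position that most improves the alpha angle would reduce the incidence of anterior impingement with videolaryngoscopy", and "We hypothesise the position that brings the alpha angle closest to 180° would reduce the incidence of anterior impingement and therefore considered best" for intubation with a videolaryngoscope.

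Section 8.3.1 gives the whole primary analysis in one sentence: ANOVA or another suitable test, with significance at p below 0.05. Section 8.3.2 does the same for beta and delta. Neither section names a pairwise contrast, an estimate, an interval, a model for three measurements on the same person, or a rule for choosing a position. Sections 1.4 and 7 have each participant scanned in all three positions, and section 8.1 sets the sample at 20 volunteers.

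Section 2.2 looks further ahead. It says "We hypothesise that the position that improves the alpha angle the most would be considered as the ideal position for videolaryngoscopy and tracheal intubation", that "this study would help us to recommend an ideal head and neck position", and that "This will further help to improve the first attempt success rate of tracheal intubation". The endpoints in sections 3.3 and 3.4 are three angles in degrees. Under section 7, a participant's involvement finishes with the last scan. Section 13 is more cautious and presents the study as an initial step towards guidance.

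**The concern.** The objective asks *which* position, but the stated analysis answers only *whether any differ*. A significant overall F test is compatible with one position ahead of two others, with two tied ahead of a third, or with three distinct means. If the report gives a p value and three means, the reader will take the position with the most favourable mean as the answer, whether or not the data separate it from the runner-up. Because no follow-up comparison is planned, its choice could be made after the data are seen.

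A smaller matter is how far the conclusion reaches. No laryngoscopy, tube passage or intubation is observed, so no sample size would let these data confirm or refute the statements about impingement, first-attempt success or overall suitability for intubation.

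**Working it through.** **Inputs from the documents.** n = 20 (section 8.1); three positions per participant (section 1.4), hence 3 pairwise contrasts; significance level 0.05 (section 8.3.1). The documents give no SD, effect size, power or correlation, so the planned n cannot be reproduced and there is no stated figure to check.

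**Assumptions.** Normal data; equal within-person correlation of 0.5 between positions; all 20 sets complete; two-sided tests. Effects are in units of SDd, the SD of the within-person difference between two positions.

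**Formulas.**
- Overall test: F = MS(position) / MS(residual) on 2 and 38 df.
- Paired contrast: t = mean difference / (SDd/√20) on 19 df.
- 95% CI half-width: t(0.975, 19) × SDd/√20 = 2.093/4.472 = 0.468 SDd.
- Bonferroni half-width: t(1 − 0.05/6, 19) × SDd/√20 = 2.625/4.472 = 0.587 SDd. Ratio 0.587/0.468 = 1.25.

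For assumed SDd of 5°, 10° and 15°, the half-widths are 2.34°, 4.68° and 7.02° unadjusted, and 2.93°, 5.87° and 8.80° with Bonferroni.

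**Step 1: what the overall test shows.** Two positions are exactly tied for best and the third is worse by d. Simulation with at least 50,000 trials per case:

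| d (SDd) | Overall F significant |
|---|---|
| 0.5 | about 60% |
| 0.75 | about 92.5% |
| 1.0 | 99.6% |

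In the same data the contrast between the two tied positions is significant in only 5% of trials. The overall test is therefore nearly always significant at 1.0 SD when there is no single best position to find.

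**Step 2: a rule that answers the objective.** Name a position only if F is significant and both of its paired contrasts favour it. Rule A tests each contrast at 0.05 after a significant F. Rule B uses Bonferroni contrasts at 0.05/3 = 0.0167, without the F gate.

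| Truth | d (SDd) | Rule A names a position | Rule B names a position |
|---|---|---|---|
| Two tied best (naming is false) | 0.5 to 1.0 | 4.5% to 5.1% | 1.4% to 1.8% |
| One truly best, other two tied | 0.5 | 39% | 21% |
| One truly best, other two tied | 0.75 | 81% | 63% |
| One truly best, other two tied | 1.0 | 98% | 92% |

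**Sanity check.** When the third position is clearly worse, F and both contrasts against it are almost always significant. False naming then reduces to one two-sided test of two equal positions: 5% under Rule A and 0.05/3 = 1.7% under Rule B, as simulated.

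**Step 3: reach of the conclusion.** Endpoints that are MRI angles: alpha, beta and delta. Endpoints that record impingement, tube passage or intubation success: none. The statements in sections 2.2 and 3.1 about those outcomes therefore lie outside the data to be collected.

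**The case against.** **The overreach is mostly hedged.** This largely stands. Both sentences in section 3.1 are marked as hypotheses, the objective is confined to the angle on MRI, section 1.4 says only that imaging would suggest a position, and section 13 is cautious. A reader might infer that the protocol claims to establish the best position clinically; the documents do not support that. A mechanistic study may state the clinical hypothesis behind it, and section 1.1 gives a mechanism: the tube is directed forwards while the trachea descends backwards, "creating an acute angle impeding passage of the tube". What remains is the recommendation sentence and the flat first-attempt sentence in section 2.2.

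**The 60% to 99.6% figures are not the plan's error rate.** This stands. They would be the false-naming rate of a rule that takes the top mean after a significant ANOVA. A reader might infer that this is the planned rule, but section 8.3.1 states none, and its open wording permits pairwise comparisons. The figures show that an overall p value does not identify a position. The fault is under-specification.

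**Bonferroni is not required.** This also stands. With three positions, a significant F before the paired tests already keeps false naming near 5%, and Bonferroni lowers the chance of naming a position that really is best.

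**The cited clinical evidence does not contradict the hypothesis.** A reader might set the trial that "studied neutral and sniffing position with no difference in success rate in tracheal intubation between two positions" against the alpha hypothesis. As reported, that trial and the study finding sniffing harder used different outcomes and devices, and neither concerns alpha. They do not settle the link between alpha and impingement.

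**Conclusion.** The concern holds as a gap in the analysis specification, worth correcting before the data are analysed. The stated overall test cannot identify a position: it is significant in 99.6% of trials of n = 20 when two positions are tied and the third is worse by 1.0 SDd. A simple pre-specified rule closes the gap, with about 5% false naming when two positions are tied, and 39%, 81% or 98% correct naming at 0.5, 0.75 or 1.0 SDd.

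The percentages rest on normality, equal within-person correlation and 20 complete sets; fewer sets would widen the intervals. Values in degrees depend on an SD that the documents do not give. The logical point, that an overall p value does not say which position is better, needs none of these assumptions.

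The wording in sections 2.2 and 3.1 is a secondary matter. It does not show a flawed design, and it calls for no new endpoint, scan or participant.

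**What to change.** **Section 8.3.1.** Specify:
- a repeated-measures ANOVA on alpha, since each participant is scanned in all three positions;
- the three mean within-person differences, each with a 95% CI;
- if any alpha exceeds 180°, analysis of the distance from 180°, because the definition in section 2.1 does not rule this out and a larger angle would then not mean a closer one;
- the naming rule: a position is reported as closest to 180° only if the overall test is significant and both of its paired contrasts favour it at 0.05; otherwise the leading positions are reported as not separated.

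Bonferroni contrasts are an acceptable, more conservative alternative. Their price is intervals about 25% wider and correct naming of 21%, 63% and 92% in place of 39%, 81% and 98%.

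**Section 8.3.2.** Show the same three differences for beta and delta, labelled secondary.

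**Sections 3.1 and 2.2, wording only.** Keep the hypotheses in section 3.1 and add that effects on impingement, first-attempt success and suitability for intubation are not tested in this study. Reword the recommendation and first-attempt sentences in section 2.2 to match the caution of section 13.

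**Cost.** One extra table from data already planned and a more modest claim, with no change to scans, endpoints or sample size. Some trials will name no single position: where one truly leads by 0.5 SDd, that happens in about 100 − 39 = 61% of them.

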3.2 Secondary objectives

The other two angle measurements include

Beta (β) angle between laryngeal (LA) and pharyngeal axes (PA). This is the alignment between line passing through the voice box and pharynx (on the MRI image line passes through the top part of second cervical vertebra)

Delta (δ) angle between pharyngeal axes (PA) and oral axes (OA). This is the alignment between pharyngeal axis and the line passing parallel to the palate.

The MRI reports will be interpreted by a Consultant Radiologist.

3.3 Primary endpoint/outcome

The alpha (α) angle in degrees.

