8.3 Statistical analysis plan

8.3.1 Primary outcome analysis

Data will be analysed using ANOVA or appropriate test and p value less than 0.05 was considered statistically significant

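### Does analysing raw alpha, when the aim is closeness to 180°, test the wrong question?

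*Combined protocol and SAP*

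**What the plan says.** All places are in the combined protocol and SAP.

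- Section 3.1 sets the aim: "The primary objective is to identify which of the three head and neck positions we have identified" improves alpha. It then gives the criterion: "We hypothesise the position that brings the alpha angle closest to 180° would reduce the incidence of anterior impingement".
- Section 3.3 gives the primary endpoint in one line: "The alpha (α) angle in degrees". No distance from 180° is derived.
- Section 8.3.1 gives the analysis: "Data will be analysed using ANOVA or appropriate test and p value less than 0.05 was considered statistically significant".
- Section 2.1 defines the angle by its two axes. For the tracheal axis: "The tracheal axis (TA) is defined as a line passing through the centre of intrathoracic part of trachea to the centre of cricoid cartilage". For the laryngeal axis: "The laryngeal axes (LA) is defined as a line passing through the centre of cricoid cartilage to the base of the epiglottis". Both run through the centre of the cricoid.
- Figure 4 in section 2.1 is captioned as showing alpha on an MRI scan. The image is not reproduced in the text used here, which is not a gap in the plan.

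**The concern.** Being closest to a value is a target, not a maximum. An ANOVA on raw alpha compares mean angles. If angles could fall on both sides of 180°, two positions equally far from straight, one at 174° and one at 186°, would differ significantly although neither is better aligned. A position averaging exactly 180° with wide scatter would look ideal although individual airways were far from straight. The positions in section 1.4 run from neck flexion to full extension, so a bend in either direction is conceivable, and the text states no side or range for reading alpha. The stake would be the primary conclusion: a small p-value that does not support a claim of better alignment, or the wrong position named as best.

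**Working it through.** **Inputs.** From the documents: the axis definitions (2.1), the 180° criterion (3.1), raw alpha as endpoint (3.3), ANOVA at 0.05 (8.3.1), 20 volunteers (8.1) and three positions each (1.4). The documents give no alpha values, so every mean and SD below, and the within-person correlation of 0.5, is an assumption.

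**Step 1: which values alpha can take.** One arm runs from the cricoid to the intrathoracic trachea, the other from the cricoid to the base of the epiglottis. If the airway is straight the arms are opposite and the angle is 180°. If it bends by b degrees, forwards or backwards, the angle between the arms is 180° − b. Two crossing lines also form a supplementary angle, for which straight would be 0°, but the 180° criterion in section 3.1 excludes that reading. So alpha ≤ 180°.

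**Step 2: the two analyses coincide.** With alpha ≤ 180°, the distance is d = |180 − alpha| = 180 − alpha for every scan, and each position mean of d is 180 minus that position's mean alpha. All deviations from means change sign only, so every sum of squares, and hence F and p, is unchanged. The largest mean alpha is the smallest mean distance. A check on a simulated 20 × 3 data set with values between 140° and 180° gave p = 0.436 for both.

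**Step 3: the damaging examples under the plain definition.** Let θ be a fixed-side reading that may pass 180°. The ordinary angle is alpha = 180 − |180 − θ|; for instance θ = 186° gives 180 − 6 = 174°. With m = |180 − mean θ| and SD s, the mean of |180 − θ| is s√(2/π)·exp(−m²/2s²) + m[1 − 2Φ(−m/s)].

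- Mean θ 174, 174 and 186, SD 6 (m = 6 in each): 6 × 0.798 × 0.607 + 6 × 0.683 = 7.00. Mean recorded alpha is 180 − 7.00 = 173.00° in all three positions. ANOVA on fixed-side θ rejects in 100% of simulated trials. ANOVA on recorded alpha is the ANOVA on |180 − θ|, which rejects in 6%.
- Mean θ 180, SD 10: 10 × 0.798 = 7.98, so mean recorded alpha is 172.02°. Mean θ 176, SD 4: 4 × 0.798 × 0.607 + 4 × 0.683 = 4.67, so 175.33°. Recorded alpha ranks the second position ahead, exactly as the distance does.

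**Step 4: what if a fixed-side convention were used after all?** Repeated-measures ANOVA, n = 20, 4,000 simulated trials per row. The last two columns give how often the chosen position differs from the one with the smallest mean distance in the same simulated trial.

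| Means; SD | Above 180° | Raw rejects | Distance rejects | Highest mean differs | Mean nearest 180° differs |
|---|---|---|---|---|---|
| 160/170/175; 5 | 6% | 100% | 100% | 0% | 0% |
| 160/170/175; 8 | 13% | 100% | 100% | 2% | 2% |
| 172/180/188; 5 | 50% | 100% | 92% | 100% | 0% |
| 172/180/188; 8 | 50% | 100% | 31% | 96% | 8% |
| 175/185/180; 8 | 50% | 100% | 10% | 82% | 34% |
| 175/185/175; 5 | 38.5% | 100% | 6% | 61% | 25% |

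In the last row no position is truly best. Large errors appear only when position means lie on both sides of 180°, and mostly under a rule that the highest mean wins. Section 3.1 has no such rule; it looks for the angle nearest 180°.

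**The case for a change.** The strongest reply is that the plan states neither a side nor a range for alpha, so a radiologist could read it on one fixed side and record values above 180°. Choosing the mean nearest 180° would then not repair the p-value, which would still test equality of mean angles and not of closeness. It would also fail under unequal spread: for mean 180, SD 10 against mean 176, SD 4 (independent draws, 20 each), it picks the first in 90% of runs although the second has the smaller average distance in 99%.

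The conditional statement stands: under fixed-side reading, with means straddling 180° or clearly unequal spreads, raw alpha and closeness part company. The condition is what fails. No section describes fixed-side reading, reports an angle above 180° or says that the airway bends in opposite directions across positions. A bend in the other direction is not enough, because the ordinary angle still records it below 180°. The examples are also extreme. At SD 6, a mean of 186° puts about 84% of that position's scans above 180°, against about 16% at a mean of 174°. The spread example needs a 2.5-fold ratio of SDs with no basis in the documents, and it presumes that average individual distance, not closeness of the mean, is what section 3.1 intends. Keeping values above 180° and then taking absolute distances would only create the difficulty and undo it again.

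**Conclusion.** The concern does not hold. With alpha read as the plain angle between two axes meeting at the cricoid, raw alpha already measures closeness to 180°. The effect of switching to |180° − alpha| is zero: same F, same p-value, same ranking. This rests on one assumption, that the ordinary angle of at most 180° is recorded. That is the natural reading of section 2.1 and fits a criterion in section 3.1 for which 180° is the ceiling. A sentence saying how alpha is read would do no harm, but the primary analysis does not depend on it. This conclusion covers only the scale of the endpoint, not the choice of test or the basis of the sample size.
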